1.8.2 Gastrointestinal Toxicity

Diarrhea has been recognized with other anti-HER2 antibodies. Per the Investigator's Brochure, diarrhea has been commonly observed when ZW25 is given as monotherapy.

As noted above, in the palbociclib plus fulvestrant arm in the PALOMA-3 study, gastrointestinal AEs occurring in $\geq 10\%$ of subjects of any grade included nausea (34%), stomatitis (28%), diarrhea (24%), and vomiting (19%). None of these gastrointestinal events were Grade 4 in severity; and, in 1% of subjects, stomatitis and vomiting were recorded as a Grade 3 event (IBRANCE[®]).

Subjects in the current study ZWI-ZW25-202 will be monitored for potential gastrointestinal toxicity by routine AE surveillance. If gastrointestinal toxicity develops during the study, prophylactic or symptomatic treatment may be considered.

1.8.3 Hematologic Toxicity

Management of hematologic toxicities includes collection of samples for hematology tests at regular intervals per the protocol. Subjects with evidence of hematologic complications should receive prompt treatment and supportive care.

No hematologic effects were observed in toxicology studies for ZW25. Per the Investigator's Brochure, anemia has been commonly reported when ZW25 is given as monotherapy. Neutropenia, the most common any-grade and Grade 3 or higher AE associated with palbociclib, is consistent with the drug's mechanism of action and can be effectively managed with dose interruption, dose reduction, or dose delay (McShane 2018). A Grade ≥ 3 decrease in neutrophil counts was reported in 66% of subjects receiving palbociclib plus fulvestrant in PALOMA-3. The median time to first episode of any grade neutropenia was 15 days and the median duration of Grade ≥ 3 neutropenia was 7 days. Febrile neutropenia has been reported in 1.8% of subjects exposed to palbociclib across PALOMA-2 (palbociclib plus letrozole) and PALOMA-3. One death due to neutropenic sepsis was observed in PALOMA-2. The most frequently reported Grade ≥ 3 adverse reactions ($\geq 5\%$) in subjects receiving palbociclib plus fulvestrant in PALOMA-3 in order of descending frequency were neutropenia and leukopenia (IBRANCE[®]).

In addition, because fulvestrant is administered IM, it should be used with caution in subjects with bleeding diathesis, thrombocytopenia and anticoagulant use.

1.8.4 Infusion-related Reactions

While ZW25 is a fully humanized antibody, infusion reactions may occur. Infusion reactions consist of a symptom complex characterized by fever and chills and may include nausea, vomiting, pain, headache, dizziness, dyspnea, hypotension, rash, and asthenia. Severe and potentially fatal reactions may include bronchospasm, anaphylaxis, angioedema, hypoxia, and severe hypotension. Infusion reactions may occur during or immediately following the initial infusion or at a later time point. While severe reactions usually occur during or immediately after infusion, onset and clinical course can be variable.

Per the Investigator's Brochure, infusion related reaction has been commonly reported when ZW25 is given as monotherapy.

A description of safety data is presented separately in the Investigator's Brochure.

Prophylaxis for and management of ZW25-related infusion reactions are provided in [Section 5.2.7.1](#) and [Section 5.2.3.2](#), respectively.

2 OBJECTIVES AND ENDPOINTS

2.1 Part 1 Objectives and Endpoints

Objectives	Endpoints

Primary:
 
 To recommend a dose for ZW25 in combination with palbociclib plus fulvestrant for Part 2 by evaluating the safety and tolerability of ZW25 in combination with palbociclib plus fulvestrant in subjects with locally advanced (unresectable) and/or metastatic HER2-positive, HR-positive breast cancer 	
 Frequency of dose-limiting toxicities (DLTs) Frequency and severity of adverse events (AEs) Frequency of serious adverse events (SAEs) and deaths Frequency and severity of clinical laboratory abnormalities Frequency of electrocardiogram (ECG) and left ventricular ejection fraction (LVEF) abnormalities Frequency and severity of adverse events of special interest (AESIs), including absolute decreases in LVEF $\geq 10\%$ points from baseline, symptomatic heart failure, infusion-related reactions, and all \geq Grade 2 events of pneumonitis and/or interstitial lung disease, including pulmonary fibrosis Frequency of dose reductions of ZW25 Frequency of dose reductions of components of combination therapy Frequency of treatment discontinuations due to AEs

Secondary:
 
 To evaluate the pharmacokinetics (PK) of ZW25 in combination with palbociclib plus fulvestrant 	
 Serum concentrations of ZW25 as a function of time post-dosing

Objectives	Endpoints

To evaluate the immunogenicity of ZW25 in combination with palbociclib plus fulvestrant	
PK parameters for single (first) dose and multiple doses of ZW25Frequency, duration, and time of onset of anti-drug antibodies (ADA) and neutralizing antibodies, if applicable

Exploratory:
 
To explore the utility of potential serum and tumor biomarkers	
Exploratory biomarkers, including but not limited to circulating tumor DNA (ctDNA), Prosigna Breast Cancer Prognostic Gene Signature Assay (hereafter referred to as ProSigna; also, formerly called the PAM50 test) and HER2 extracellular domain (HER2 ECD)

2.2 Part 2 Objectives and Endpoints

Objectives	Endpoints
Primary:	

 To evaluate the anti-tumor activity of ZW25 in combination with palbociclib plus fulvestrant in subjects with locally advanced (unresectable) and/or metastatic HER2-positive, HR-positive breast cancer 	
 Progression-free survival 6 (PFS6, defined as the % of mITT subjects with PFS \geq 24 weeks)
Secondary:	

 To evaluate additional measures of the anti-tumor activity of ZW25 in combination with palbociclib plus fulvestrant in subjects with locally advanced (unresectable) and/or metastatic HER2-positive, HR-positive breast cancer To evaluate the safety and tolerability of ZW25 in combination with palbociclib plus fulvestrant To evaluate the PK of ZW25 in combination with palbociclib plus fulvestrant To evaluate the immunogenicity of ZW25 in combination with palbociclib plus fulvestrant 	
 Objective response rate (ORR) Duration of response (DOR) Disease control rate (DCR) Progression-free survival (PFS) Overall survival (OS) Frequency and severity of AEs Frequency of SAEs and deaths Frequency and severity of clinical laboratory abnormalities Frequency of ECG and LVEF abnormalities Frequency and severity of AESIs, including absolute decreases in LVEF \geq 10% points from baseline, symptomatic heart failure, infusion-related reactions, and all \geq Grade 2 events of pneumonitis and/or interstitial lung disease, including pulmonary fibrosis Frequency of dose reductions of ZW25 Frequency of dose reductions of components of combination therapy Frequency of treatment discontinuations due to AEs Serum concentrations of ZW25 as a function of time post-dosing PK parameters for single (first) dose and multiple doses of ZW25 Frequency, duration, and time of onset of ADA and neutralizing antibodies, if applicable
Exploratory:	

 To explore the utility of potential serum and tumor biomarkers 	
 Exploratory biomarkers, including but not limited to ctDNA, ProSigna, and HER2 ECD

3 INVESTIGATIONAL PLAN

3.1 Summary of Study Design

This is a multicenter, Phase 2a, open-label, 2-part study to investigate the safety, tolerability, and anti-tumor activity of ZW25 in combination with palbociclib (**IBRANCE[®]**), an inhibitor of

CDK4 and CDK6) plus fulvestrant (**FASLODEX[®]**), an ER antagonist). Premenopausal women and perimenopausal women will also be treated with a LHRH analogue (also known as gonadotropin-releasing hormone analogue) per institutional guidelines. Eligible subjects include those with locally advanced (unresectable) or metastatic HER2-positive, HR-positive breast cancer.

[figure not shown]
For both parts of the study, subjects must have a diagnosis of locally advanced (unresectable) and/or metastatic HER2-positive, HR-positive (ER-positive and/or progesterone receptor-positive [PgR-positive]) breast cancer. Eligibility will be determined based on local (institutional) review of HER2 status, HR status, and disease pathology, with subsequent retrospective central review for HER2 status. HER2 expression will be determined based on the HER2 Testing in Breast Cancer: American Society of Clinical Oncology (ASCO)/College of American Pathologists (CAP) Clinical Practice Guidelines ([Wolff 2018](#)). Hormone receptor status will be determined based on the ASCO/CAP Guideline Recommendations for Immunohistochemical Testing of Estrogen and Progesterone Receptors in Breast Cancer ([Hammond 2010](#)). If the local assessments at a particular site cannot be done with these tests and to these standards, then central assessment will be required before a subject can be enrolled.

Part 1 of the study will first evaluate the safety and tolerability of ZW25 in combination with palbociclib plus fulvestrant and will confirm the recommended doses of ZW25, palbociclib, and fulvestrant when given in combination. Then, Part 2 of the study will evaluate the anti-tumor activity of the recommended dose level of the combination of ZW25 with palbociclib plus fulvestrant in subjects with HER2-positive, HR-positive breast cancer.

The overall study design is presented in [Figure 2](#). Each treatment cycle of ZW25 combined with palbociclib plus fulvestrant is 28 days. If any component(s) of the combination therapy is discontinued due to toxicity deemed related to the component(s), subjects on either part of the study may continue to receive the other component(s) of the study regimen until disease progression or start of subsequent anticancer therapy. (Note: trastuzumab, alternate CDK4/6 inhibitors, or any other treatment not part of the study regimen will be considered subsequent anticancer therapy. Palliative radiotherapy to a non-target bone lesion that is not progressing is allowed after the second cycle of treatment and must be administered after the initial response assessment obtained per protocol. This will not be considered subsequent anticancer therapy but must not interfere with the assessment of tumor target lesions. Treatment with palbociclib should be interrupted during palliative radiotherapy). Subjects who discontinue treatment with all 3 drugs for any reason (except death or withdrawal of consent) on either part of the study will have an end-of-treatment (EOT) visit within 14 days after the last dose of study drug (ZW25, palbociclib, and/or fulvestrant) and safety follow-up visit at approximately 30 days after the last dose of study drug. Subjects who discontinue all study treatment on either part of the study for reasons other than progressive disease or start of subsequent anticancer therapy will continue in follow-up with disease assessments approximately every 8 weeks after the previous scan until disease progression or start of subsequent anticancer therapy. If subjects enter this follow-up period before 24-weeks have elapsed since the start of study treatment, a disease assessment must be done at 24-weeks from the start of treatment (not required if ≤ 4 weeks since last disease assessment or if disease progression has already been documented). Responses that are initially observed during this follow-up period should be confirmed with disease assessment 4 weeks (+1

week) later. Following progression or start of subsequent anticancer therapy, disease assessments will be discontinued and subjects will enter long-term follow-up for survival status. Data on survival will be collected via clinic visits (if feasible) or via telephone calls every 3 months after the last follow-up visit. Subjects may be discontinued from the study due to death, lost to follow-up, consent withdrawal or study termination by sponsor. Reason for study discontinuation will be recorded. The same assessment schedule ([Appendix A](#)) will be used for subjects in both parts of the study. All subjects in Part 1 will have blood samples taken per the extensive sampling schedule ([Appendix B](#)). In Part 2, at least 6 subjects will have blood samples taken per the extensive sampling schedule ([Appendix B](#)) while the remaining subjects will have samples taken based on the sparse sampling schedule ([Appendix C](#)).

Figure 2: Overall Study Design

CT = computed tomography; D = day; MRI = magnetic resonance imaging; Q8W = every 8 weeks.

Note: On Days 1 and 15 of each cycle, ZW25 will be administered first followed by palbociclib and fulvestrant.

Note: The DLT-evaluation period will be the initial 28 days of treatment beginning Cycle 1 Day 1.

*, Subjects who discontinue treatment with all 3 drugs for any reason (except death or withdrawal of consent) on either part of the study will have an end-of-treatment (EOT) visit within 14 days after the last dose of study drug and safety follow-up visit at approximately 30 days after the last dose of study drug.

**, Subjects who discontinue all study treatment for reasons other than progressive disease or start of subsequent anticancer therapy will continue in follow-up with disease assessments approximately every 8 weeks after the previous scan until disease progression or start of subsequent anticancer therapy.

***, Following progression or start of subsequent anticancer therapy, disease assessments will be discontinued and subjects will enter long-term follow-up for survival status. Data on survival will be collected approximately every 3 months after the last follow-up visit.

For all subjects, computed tomography (CT) and/or magnetic resonance imaging (MRI) scans will be performed for tumor restaging every 8 weeks timed from Cycle 1 Day 1 during treatment and will be assessed according to the revised RECIST guideline version 1.1 ([Eisenhauer 2009](#)). Initial responses should be confirmed, if feasible, with repeat scans 4 weeks (+1-week window) following initial documentation of objective response. The schedule of response assessments should not be adjusted after the confirmatory scan and should maintain the schedule of every 8 weeks timed from Cycle 1 Day 1. The same imaging modality should be used throughout the

study as was used at baseline. Data on breast cancer serum tumor markers, if monitored, should also be collected at the time of disease assessment.

Subjects' safety will be monitored at predetermined time points by recording the type, frequency, and severity of AEs graded using the National Cancer Institute Common Terminology Criteria for Adverse Events (NCI CTCAE) version 5.0 (27 November 2017), including AESIs, SAEs and deaths, clinical laboratory values (including hematology and serum chemistry), physical examination, vital signs (blood pressure, heart rate, respiratory rate, and temperature), body weight, and ECOG performance status. Cardiac function will be monitored via 12-lead ECG and echocardiogram or multiple gated acquisition scan (MUGA). AEs will be collected from the start of dosing of any study drug on Cycle 1 Day 1 time of consent through 30 days after last dose of study drug (ZW25, palbociclib, and/or fulvestrant). Study protocol-related AEs are to be collected from the time of informed consent. All investigators should follow subjects with SAEs until the event returns to baseline, the event stabilizes (recovering/resolving) or is no longer considered clinically significant by the investigator, or the subject dies or withdraws consent. Treatment-emergent AESIs should continue to be followed until resolution or return to baseline and include absolute decreases in LVEF ≥ 10 percentage points from baseline, symptomatic heart failure, infusion-related reactions, and all \geq Grade 2 events of pneumonitis and/or interstitial lung disease, including pulmonary fibrosis.

Safety and study conduct will be monitored throughout the study by the Safety Monitoring Committee (SMC) (Section 3.1.3).

In both parts of the study, subjects may continue on study treatment until radiographically -confirmed disease progression as defined by RECIST version 1.1, clinical disease progression, unacceptable toxicity, consent withdrawal, physician decision, pregnancy, protocol violation, start of a subsequent anticancer therapy (Note: trastuzumab, alternate CDK4/6 inhibitors, or any other treatment not part of the study regimen will be considered subsequent anticancer therapy. Palliative radiotherapy to a non-target bone lesion that is not progressing is allowed after the second cycle of treatment and must be administered after the initial response assessment obtained per protocol. This will not be considered subsequent anticancer therapy but must not interfere with the assessment of tumor target lesions. Treatment with palbociclib should be interrupted during palliative radiotherapy) or study termination by the sponsor. Clinical progression is defined as worsening or re-emergence of pre-existing symptoms relating to underlying cancers, or emergence of new symptoms that cannot be attributed to drug toxicities or alternative causes. Every effort should be made to confirm disease progression radiographically.

If any component(s) of the combination therapy is discontinued due to toxicity deemed related to the component(s), subjects ZW25 on either part of the study may continue to receive the other component(s) of the study regimen until disease progression or start of subsequent anticancer therapy. Subjects who discontinue treatment with all 3 drugs for any reason (except death or withdrawal of consent) on either part of the study will have an end-of-treatment (EOT) visit within 14 days after the last dose of study drug (ZW25, palbociclib, and/or fulvestrant) and safety follow-up visit at approximately 30 days after the last dose of study drug.

3.1.1 Part 1 Safety Evaluation

The primary objective of Part 1 is to characterize the safety and tolerability of ZW25 in combination with palbociclib plus fulvestrant. In addition, Part 1 will confirm the recommended doses for all the drugs in this combination.

ZW25 will be administered IV at the initial dose of 20 mg/kg Q2W, which is a single-agent RD identified in Study ZWI-ZW25-101. Palbociclib will be administered PO with food at 125 mg QD for the first 21 days of each 28-day cycle. Fulvestrant will be administered as an IM injection at 500 mg Q2W for the first 3 doses, then Q4W thereafter. A step-down dose level of ZW25 (e.g., 15 mg/kg [or other dose level not lower than 15 mg/kg] Q2W) and/or palbociclib (e.g., 100 mg PO and/or 75 mg PO QD) may be allowed if recommended by the SMC. Subjects will also receive LHRH analogue treatment per institutional guidelines. The DLT-evaluation period will be the initial 28 days of treatment beginning on Cycle 1 Day 1.

Initially, up to 6 evaluable subjects will be assessed at a ZW25 monotherapy RD of 20 mg/kg Q2W in combination with palbociclib plus fulvestrant; therefore, at least 6 evaluable subjects will be enrolled in Part 1 of the study and up to approximately 36 evaluable subjects if all step-down doses of ZW25 and palbociclib are evaluated (see [Section 9.1](#) for possible dose combinations). The SMC may decide if more than 6 subjects may be enrolled in a given dose level to better characterize the safety profile of a particular dose level.

Prior to dosing with ZW25, all subjects should receive prophylactic treatment for infusion reactions ([Section 5.2.7.1](#)). Additional premedications may be given for palbociclib and fulvestrant per institutional standards and/or the local prescribing information.

The recommended doses for all drugs in this combination (ZW25 in combination with palbociclib plus fulvestrant) will be confirmed based on the evaluation in [Section 3.1.2](#).

[figure not shown]
3.1.2 Dose-Limiting Toxicity Evaluation and Determination of Recommended Dose Level (Part 1 only)

The DLT-evaluation period will be the first 28 days of treatment.

The dose level (evaluated dose of ZW25 plus evaluated dose of palbociclib and fulvestrant) will be considered not tolerated if ≥ 2 of 6 DLT evaluable subjects experience a DLT. If DLTs are observed in ≥ 2 subjects, the SMC may recommend a step-down dose level of 15 mg/kg Q2W or other dose not lower than 15 mg/kg Q2W for evaluation in up to 6 additional DLT evaluable subjects. Additionally, the SMC may recommend evaluation of step-down doses of palbociclib of 100 mg PO QD and/or 75 mg PO QD with or without recommending evaluation of a step-down dose of ZW25. There is no step-down dose for fulvestrant at a cohort or study population level; however, individual subjects who develop moderate hepatic impairment (Child-Pugh Class B) while on study treatment will have their fulvestrant dose reduced to 250 mg. Intermediate dose levels of ZW25 and/or palbociclib may also be recommended by the SMC. The SMC may recommend step-down doses for 1 or more of the drugs in the combination regimen at any time based on the overall safety profile. The dose of ZW25 is allowed to be de-escalated by a maximum of 1 step-down dose as recommended by the SMC. The dose of

palbociclib is allowed to be de-escalated by a maximum of 2 step-down doses as recommended by the SMC. At a reduced dose level, if 1 or fewer of the 6 subjects experience a DLT, then the dose level may be confirmed as recommended for Part 2. When necessary, more than 6 subjects may be enrolled in a given dose level to better characterize the safety profile of a particular dose level. The study will advance to Part 2 based on SMC recommendation. The DLT evaluation schema is presented in Figure 3. Additional safety experiences in later cycles may be considered when confirming the recommended dose level (ZW25 in combination with palbociclib plus fulvestrant) for Part 2.

Figure 3: DLT Evaluation Schema (Part 1 Only)

DLT= dose-limiting toxicity; RD=recommended dose; SMC=Safety Monitoring Committee

*The roles, responsibilities and functioning of the SMC are described in more details in the SMC charter.

** Step-down dose levels of ZW25 and/ or palbociclib as recommended by the SMC.

A subject will be considered DLT-evaluable if he/she has received $\geq 75\%$ of the planned total dose of each component of study treatment (ZW25, palbociclib, and fulvestrant) over the first 28 days of treatment, and was followed for the full DLT evaluation period, unless the reason for not receiving required doses or not being followed was the occurrence of a DLT. If the reason for not receiving required doses is a DLT, a subject will still be considered evaluable. To account for potential discontinuations prior to being evaluable for DLT (for example, progressive disease [PD] or subject preference), enrollment of replacement subjects will be allowed to permit assessment of DLTs and recommended dose level for Part 2.

Dose-limiting toxicities, defined using the (NCI CTCAE) version 5.0, are events that 1) occur following administration of ZW25, palbociclib, and fulvestrant, or any combination of ZW25 and 1 or more of these drugs; and 2) meet the criteria described below. Events for which there is an alternative clinical explanation (e.g., clearly related to an intercurrent illness, disease progression, or extraneous causes) will not be considered DLTs. The relationship of AEs to each component of study treatment will be determined by the investigator; however, the Sponsor and/or the SMC may query the relationship assessments and/or determine that the event was related to additional components of the regimen.

DLT Criteria Non-Hematologic

Any non-hematologic AE \geq Grade 3 in severity that is not clearly and incontrovertibly due to disease progression or extraneous causes (e.g., accidental injury or similar event) is considered a DLT, with the following exceptions:

- Grade 3 fatigue lasting ≤ 3 days
- Grade 3 diarrhea, nausea, or vomiting that resolves to \leq Grade 1 or baseline within 3 days with adequate supportive care
- Grade 3 rash without maximal use of corticosteroids or anti-infectives
- Infusion reaction \leq Grade 3 (for management of infusion reactions, see [Section 5.2.3.2](#))

Grade 2 or greater events of pneumonitis and/or interstitial lung disease, including pulmonary fibrosis not clearly and incontrovertibly related to disease progression or extraneous causes is considered a DLT.

Any laboratory abnormality \geq Grade 4 not clearly and incontrovertibly due to disease progression or extraneous causes is considered a DLT. Any asymptomatic \geq Grade 3 electrolyte abnormality that lasts > 72 hours or any symptomatic \geq Grade 3 electrolyte abnormality of any duration is considered a DLT. Amylase and lipase elevations not associated with symptoms or clinical manifestations of pancreatitis are not considered DLTs.

Any clinically relevant toxicities not clearly and incontrovertibly due to disease progression or extraneous causes and that do not resolve to \leq Grade 1 or baseline within 2 weeks may be considered a DLT based upon review by the study SMC.

Greater than a 2-week delay in the start of Cycle 2 due to unresolved toxicity not clearly and incontrovertibly due to disease progression or extraneous causes will be considered a DLT.

Any death not clearly due to the underlying disease or extraneous causes is considered a DLT.

Hematologic DLT Criteria

The following hematologic AEs that are not clearly and incontrovertibly due to disease progression or extraneous causes (e.g., accidental injury or similar event) are considered DLTs:

- Absolute neutrophil count (ANC) of Grade 3 or 4 with fever (fever must be present for the Grade 3 or 4 ANC to be considered a DLT, and is defined as a temperature of $\geq 38.5^{\circ}\text{C}$)
- ANC of $< 500/\mu\text{L}$ that persists for >7 days or growth factor support for ANC $< 500/\mu\text{L}$
- Grade 3 thrombocytopenia associated with significant bleeding (requiring blood and/or platelet transfusion)
- Grade 4 thrombocytopenia
- Grade 4 anemia

Hepatic DLT Criteria

The following hepatic AEs that are not clearly and incontrovertibly due to disease progression or extraneous causes (e.g., accidental injury or similar event) are considered DLTs:

- Grade ≥ 3 elevation of transaminases (alanine transaminase [ALT] or aspartate transaminase [AST]) that is NOT thought to be due to disease progression or other medical illness
- For subjects with documented hepatic metastases and a baseline AST or ALT $> 3x$ upper limit of normal (ULN) an increase of AST or ALT $> 8x$ ULN or AST or ALT $> 5x$ ULN for ≥ 14 days that is NOT thought to be due to disease progression or other medical illness
- Grade 3 or 4 elevation of bilirubin irrespective of transaminases that is NOT thought to be due to disease progression or other medical illness
- Any single instance of AST or ALT $> 3 \times$ ULN AND total bilirubin $> 2 \times$ ULN that is NOT thought to be due to disease progression or other medical illness
- For subjects with documented hepatic metastases and a baseline AST or ALT $> 3x$ upper limit of normal (ULN) any single instance of AST or ALT $> 5 \times$ ULN AND total bilirubin $> 2 \times$ ULN that is NOT thought to be due to disease progression or other medical illness

The guidelines for assessment of Drug-Induced Liver Injury are described in [Appendix F](#).

Cardiac DLT Criteria

The following cardiac AEs that are not clearly and incontrovertibly due to disease progression or extraneous causes (e.g., accidental injury or similar event) are considered DLTs:

- LVEF below institutional limits and $\geq 10\%$ points below pre-treatment baseline

- Grade 2 symptomatic heart failure

The first DLT will result in withholding of the drug until recovery of the ejection fraction to prior levels. If subjects remain off ZW25 for more than 4 weeks they will be removed from the study. For the management of left ventricular dysfunction, see [Section 5.2.3.1](#).

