3.1.3 Safety Monitoring Committee (SMC)

Safety and study conduct will be monitored throughout the study by the SMC, consisting of the study investigators and the sponsor responsible medical expert and biostatistician. The committee is tasked with monitoring the safety of participants in this study through regular or ad hoc meetings.

SMC activities related to evaluation of DLTs, recommending step-down dose levels for ZW25 and palbociclib, and recommending the doses for all the drugs in this combination to be used in Part 2 are described in [Section 3.1.2](#).

The SMC activities will be described in and governed by the SMC Guidelines.

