5.2.2 Dose and Administration of ZW25

Dosing for ZW25 will be given as follows:

- Part 1:
 - 20 mg/kg IV ZW25; dosing Q2W on Days 1 and 15 of each 28-day cycle. Up to 1 step-down dose level (15 mg/kg Q2W or other dose not lower than 15 mg/kg Q2W) may be evaluated if recommended by the SMC and approved by the sponsor
- Part 2:
 - Recommended dose of ZW25 as confirmed in Part 1 for administration in combination with palbociclib and fulvestrant

Dosing is based on the subject's actual body weight taken at screening visit. Doses must be adjusted for subjects who experience a $\geq 10\%$ change in weight from baseline/ screening visit on dosing day. Subject weight must be measured on all ZW25 dosing days as part of the physical exam (within a window of 3 days prior to dosing). Detailed instructions for dose preparation are provided in the Pharmacy Manual.

ZW25 should be administered prior to any component of the combination chemotherapy regimen. Please refer to the Pharmacy Manual for infusion times. Subjects who experience a Grade 1 or Grade 2 infusion reaction may resume infusion of drug at a reduced infusion rate (50% slower than initial rate). All subjects should receive prophylactic treatment for infusion reactions prior to ZW25 dosing as outlined in [Section 5.2.7.1](#).

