5.2.3 Dose Modifications of ZW25

An individual subject who experiences an event that meets the criteria for DLT (defined in [Section 3.1.2](#)) at any time on study treatment may continue at a step-down dose (or an intermediate dose level determined by the SMC) once the toxicity has returned to Grade 1 or baseline with approval of the medical monitor. If the subject then experiences another such event at the step-

down dose level, with approval from the medical monitor, the dose of ZW25 administered to that individual subject should be reduced again but should not go below 10 mg/kg Q2W.

For Part 2 of the study, dose modifications for ZW25-associated toxicity are presented in [Table 5](#) below. Dose decreases or delays for other reasons may be permitted with approval from the medical monitor. The reason for dose decrease or delay must be recorded, and the sponsor must be notified. Up to 2 dose reductions per subject will be allowed for Q2W dosing, but the reduced dose cannot be lower than 10 mg/kg Q2W.

There must be a minimum of 10 days (± 2 days) between doses. Day 15 doses not administered within 6 days after Day 15 must be skipped.

Note: Although only 1 step-down dose level (not lower than 15 mg/kg Q2W) of ZW25 is allowed in the study at a cohort level, individual subjects may have up to 2 dose reductions as long as the reduced dose is not lower than 10 mg/kg Q2W.

Table 5: Recommended Management and Potential Dose Modifications for ZW25-Associated Toxicity

Adverse Event Related to ZW25	Action for ZW25
Grade 1 or Grade 2 nausea and vomiting	
 • Suggest a 5-hydroxytryptamine (5-HT₃) receptor antagonist until resolution of symptoms, or a prochlorperazine. • No dose modification of ZW25 is required. • For breakthrough nausea or vomiting, consider olanzapine 5 or 10 mg daily for three days. For subjects already receiving olanzapine, prochlorperazine may be used.

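### Does a DLT criterion that can only be met about Day 44 break the 28-day DLT evaluation in Part 1?

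*Combined protocol and SAP*

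**What the plan says.** Section 3.1.2 opens with the time frame: "The DLT-evaluation period will be the first 28 days of treatment". A dose level is not tolerated if at least "2 of 6 DLT evaluable subjects experience a DLT". A subject is DLT evaluable after receiving at least 75% of the planned dose of each drug over those 28 days and meeting a follow-up condition, with an exception where a DLT was the cause: "was followed for the full DLT evaluation period, unless the reason for not receiving required doses or not being followed was the occurrence". Table 12 (Section 9.2) repeats this for the DLT Evaluable Set, and Section 9.3.9.2 reports DLT frequency on that set. Section 9.1 allows non-evaluable subjects to be replaced and sets no time point.

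Among the DLT criteria in Section 3.1.2 is "Greater than a 2-week delay in the start of Cycle 2 due to unresolved toxicity". Unlike the criterion just before it, which leaves classification to the Safety Monitoring Committee (SMC), this one is mandatory.

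Two further provisions bear on timing. Section 3.1.2 adds that "Additional safety experiences in later cycles may be considered when confirming the recommended dose level". Section 5.2.3 says that an individual whose event meets DLT criteria "at any time on study treatment may continue at a step-down dose", subject to recovery and medical monitor approval. On procedure, Section 3.1.3 states: "The SMC activities will be described in and governed by the SMC Guidelines".

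**The concern.** A mandatory DLT that can never occur inside the stated DLT period looks like a contradiction. DLT frequency is a primary endpoint of Part 1, and it feeds the dose level given to about 50 subjects in Part 2. If a cohort were closed on Day 28, a subject could be recorded as evaluable without a DLT, or as non-evaluable and replaced, and then meet a DLT criterion about two weeks later. With one DLT among the other five subjects, the same data could be reported as 1/6, as 2/6 (not tolerated), or as 2/7 if a replacement without a DLT had already been enrolled. Section 5.2.3 does not settle this, because it governs an individual's ZW25 dosing rather than the cohort count.

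**Working it through.** **Calendar.** Cycles last 28 days (Section 3.1). Appendix A, footnote c, puts Cycle 2 Day 1 at Day 29, and the Appendix A table gives a window of ±2 days. A delay of exactly 14 days ends on Day 29 + 14 = Day 43, so more than two weeks is first reached on Day 44. From the window edges (Days 27 and 31) the result is Day 42 and Day 46. This is 14 to 18 days after Day 28. Day 42 is only a formal lower bound, since delay is more naturally counted from Day 29 or later.

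**Evaluability.** For ZW25 the plan is "dosing Q2W on Days 1 and 15 of each 28-day cycle", so one skipped dose leaves 1/2 = 50%. Fulvestrant falls on Days 1 and 15 of Cycle 1, again 1/2 = 50% if one dose is missed. Palbociclib stopped from Day 15 gives 14/21 = 67%. All are below 75%. A subject under-dosed for a toxicity that is not yet a DLT is therefore non-evaluable on Day 28. A fully dosed subject followed to Day 28 is already evaluable, and only the DLT status stays open.

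**The plan's own figures.** Table 10 is binomial with n = 6. At 30% incidence:
- P(0) = 0.7^6 = 0.118
- P(≤1) = 0.118 + 6 × 0.3 × 0.7^5 = 0.420
- P(≥2) = 0.580

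The table gives 0.12, 0.42 and 0.58. All 15 cells reproduce to two decimals.

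**What one event changes.** The cohort result turns on it only if exactly one of the other five subjects has a DLT, with probability 5p(1−p)^4: 0.20, 0.33, 0.41, 0.36 and 0.26 at p = 5%, 10%, 20%, 30% and 40%. Exact 95% intervals for the three possible reports are 0.4–64% (1/6), 4–78% (2/6) and 4–71% (2/7).

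**Illustration under an assumption.** The protocol gives no rate h for DLTs met only through the delay. With p the probability of a DLT on other grounds, the chance that such events move a cohort from at most one DLT to at least two is P(≥2; p+h) − P(≥2; p), n = 6:

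| assumed h | p = 5% | 10% | 20% | 30% | 40% |
|---|---|---|---|---|---|
| 1% | 0.013 | 0.020 | 0.025 | 0.021 | 0.015 |
| 2% | 0.028 | 0.041 | 0.049 | 0.042 | 0.030 |
| 5% | 0.082 | 0.109 | 0.121 | 0.101 | 0.070 |

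**The provisions side by side.** Section 3.1.2 defines DLTs as events following administration of the study drugs that meet the listed criteria, and gives no last day. The at-least-2-of-6 count refers to subjects who experience a DLT, also with no last day. The exception that keeps an under-dosed subject evaluable when a DLT was the reason has none either. The delay criterion names Cycle 2, so it was written to mature after Day 28. The specific criterion therefore qualifies the general 28-day period.

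The under-dosed case has a second route. The criterion just above the delay criterion lets the SMC classify as a DLT any clinically relevant toxicity not resolved to Grade 1 or baseline within two weeks. A toxicity present on Day 15 and still unresolved reaches that point at Day 15 + 14 = Day 29, without waiting for Day 44.

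**Neighbouring criteria.** The first scheduled post-baseline LVEF scan is at Cycle 3 Day 1 (Day 57, ±7 days), so the LVEF criterion also has no scheduled measurement inside the 28 days. It still operates afterwards through Section 5.2.3. For prolonged neutropenia, Section 5.3.4.1 provides blood counts as clinically indicated and suggests considering a repeat a week after Grade 3, and Appendix A, footnote f, lets the Cycle 2 Day 1 draw be taken up to 3 days early. Neither adds a counting problem that needs a change.

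**The case for a change.** The best argument for a change is that the natural reading is only an inference. No sentence says that the cohort call waits for a pending Cycle 2, that replacement is held meanwhile, or that a subject non-evaluable on Day 28 becomes evaluable again on Day 44. The later-cycle sentence is permissive and concerns confirming the dose level, not the count. The route is also plausible: Section 1.8.3 cites Grade 3 or higher neutrophil decreases in 66% of subjects on palbociclib plus fulvestrant, and afebrile Grade 3 neutropenia is not itself a DLT.

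The silence is real, and that part stands. The consequence is weaker. Section 1.8.3 also gives a median duration of 7 days for Grade 3 or higher neutropenia, so holds beyond two weeks should be uncommon. Section 3.1.2 illustrates replacement with discontinuation for progression or subject preference; a subject on a toxicity hold has not discontinued, and Section 9.1 only permits replacement. The SMC includes the study investigators, who would know that a subject's Cycle 2 is on hold, and Part 2 starts only on the SMC's recommendation. A 2/7 report needs under-dosing, early replacement, the same toxicity persisting past Day 43, and exactly one other DLT.

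**Conclusion.** No change to the plan follows. The dates are right: the criterion is first met on about Day 44, outside the 28-day period. But the protocol does not contain two opposed rules. Read together, its provisions count the delay as a DLT and keep the subject evaluable, and a competent SMC and analyst would wait for a Cycle 2 start held for toxicity. The only remedy would be to write down a rule the text already supports.

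The size is one subject's classification in an uncommon situation. The figures of 1.3% to 12.1% rest on assumed rates and are upper bounds: they presume the event is ignored and that the SMC disregards later safety.

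The conclusion assumes that the missed dose and the delayed cycle share one toxicity, so that the evaluability exception applies. Figure 3 (the DLT evaluation schema) could not be seen in the copy examined and the SMC charter or Guidelines were not available; either may state the closing point outright.
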